## 10.4 Percent Predicted Derived Variables

### Muscle Strength

Note: Many of the HHD derived variables detailed below rely on regression equations that have predictor variables in units different than what is found in the analysis datasets. Care will be taken to convert dataset variables to the correct units before they are entered into the prediction equation. The resulting predicted value will then, in turn, be converted to the appropriate unit for analysis.

### Hand-Held Dynamometry

#### Shoulder abduction and hip abduction

Regression Equations and Multiple Correlations of Sex, Age, and Weight with Muscle Strength

Muscle Action	Side	Equation*	R	R 
Shoulder Abduction	Nondominant	$165.16 - 74.9S - .910A + .126W$	.843	.710
	Dominant	$178.90 - 77.1S - 1.128A + .134W$	.843	.710
Hip Abduction	Nondominant	$203.32 - 73.3S - 1.247A + .192W$	.794	.630
	Dominant	$195.24 - 62.4S - 1.184A + .198W$	.764	.584

(Bohannon 1997b)

\*Muscle strength results in Newtons (N). S, sex (male=0, female=1); A, age (years); W, weight (Newtons).

**Note:** Age and weight values collected at the Baseline visit will be used for the calculation of predicted values for shoulder abduction and hip abduction for all study time points.

### Hip adduction

Muscle Action	Gender	Side	Age (years)	Equation
Hip Adduction	Female	Left	$\leq 55$	$19.1 - 0.30*(age - 55)$
	Female	Right	$\leq 55$	$19.5 - 0.00*(age - 55)$
	Female	Left	$> 55$	$19.1 - 0.212*(age - 55)$
	Female	Right	$> 55$	$19.5 - 0.245*(age - 55)$
Hip Adduction	Male	Left	$\leq 49$	$31.8 + 0.044*(age - 49)$
	Male	Right	$\leq 49$	$31.6 - 0.082*(age - 49)$
	Male	Left	$> 49$	$31.8 - 0.280*(age - 49)$
	Male	Right	$> 49$	$31.6 - 0.206*(age - 49)$

(Stoll et al. 2000)

Median strength results in kiloponds (kp) also known as kilogram-force (kgf)

**Note:** The age category that applies for a subject at the Baseline visit will be used for the calculation of hip adduction predicted values for all study time points.

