7.3.1 Inclusion Criteria

The criteria below should be applied to all patients who are screened for the study.

Individuals eligible to participate in this study must meet all of the following criteria:

- 1) Male or female, aged 18 – 55 years, inclusive
- 2) Willing and able to provide written, signed informed consent after the nature of the study has been explained, and before any research-related procedures are conducted
- 3) Have a documented diagnosis of GNEM, HIBM, DMRV, or Nonaka disease due to previously demonstrated mutations in the gene encoding the GNE/MNK enzyme (genotyping will not be conducted in this study)

- 4) Able to provide reproducible force in elbow flexors (i.e. two dynamometry force values with no more than 15% variability in the dominant arm) at Screening
- 5) Able to walk a minimum of 200 meters during the 6MWT at Screening without the use of assistive devices, including a cane, crutch(es), walker, wheelchair or scooter (AFOs are permitted)
- 6) Willing and able to comply with all study procedures
- 7) Participants of child-bearing potential or with partners of child-bearing potential who have not undergone a bilateral salpingo-oophorectomy and are sexually active must consent to use a highly effective method of contraception as determined by the site investigator (i.e. oral hormonal contraceptives, patch hormonal contraceptives, vaginal ring, intrauterine device, physical double-barrier methods, surgical hysterectomy, vasectomy, tubal ligation, or true abstinence [when this is in line with the preferred and usual lifestyle of the subject], which means not having sex because the subject chooses not to), from the period following the signing of the informed consent through 3 months after last dose of study drug
- 8) Females of childbearing potential must have a negative pregnancy test at Screening and be willing to have additional pregnancy tests during the study. Females considered not of childbearing potential include those who have been in menopause for at least two years, have had tubal ligation at least one year prior to Screening, or who have had a total hysterectomy or bilateral salpingo-oophorectomy

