#### 4.4 Tertiary Efficacy Endpoints

- Upper Extremity Composite Percent Predicted: The percent predicted total force values will be determined based on reference equations adjusting for age, gender, height, and weight. The percent predicted force will be calculated for each side and the bilateral percent predicted values will be averaged for each upper extremity muscle group. The mean of the four averages in percent predicted scores will be calculated for each subject to create a percent predicted UEC score, and analyzed relative to baseline to create a UEC mean change in percent predicted score.
- Lower Extremity Composite Percent Predicted: The percent predicted total force values will be determined based on reference equations adjusting for age, gender, height, and weight. The percent predicted force will be calculated for each side and the bilateral percent predicted values will be averaged for each lower extremity muscle group. The mean of the five averages in percent predicted scores will be calculated for each subject to create a percent predicted LEC score, and analyzed relative to baseline to create a LEC mean change in percent predicted score.
- Muscle strength (Total Force in kg)) for Each Individual Muscle Group: Bilateral total force for each individual muscle group included in the UEC and LEC will be reported.
- Percent Predicted in Each Individual Muscle Group: Bilateral total force for each individual muscle group included in the UEC and LEC.
- Percent of Predicted Muscle Strength in Each Individual Muscle Group: Bilateral percent predicted total force for each individual muscle group included in the UEC and LEC.
- Percent Predicted in knee extensors: Bilateral percent predicted total force of knee extensors.
- Total Score on the GNEM-FAS
- Self-Care Domain Score on the GNEM-FAS
- Individual Neuromuscular Quality of Life Questionnaire: A 45-item self-report questionnaire with 4 domains on the impact of key muscle disease symptoms on the ability to perform basic activities of daily living, functional independence, relationships and overall well-being will be administered. The individual domain scores will be calculated.
- Clinical Global Impression Scale: Investigator assessment of severity of subject's GNEM using the CGI-improvement scale (CGI-I) during treatment, in 3 target areas.
- Creatine Kinase Levels: CK levels in serum will be measured to assess the degree of reduction of CK levels observed as a surrogate for muscle injury.

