### 5.3 Muscle Strength

The highest value of the three measurements collected for each muscle will be used for all HHD endpoints.

- **HHD Individual Muscle Strength Average Score** is calculated as the average of the right and left raw measurements in kg for an individual muscle group: individual muscle strength raw score = (left-side measurement + right-side measurement) / 2. If a value from the right or left side of an individual muscle group is missing, the missing value will be imputed using the non-missing value from the other side.
- **HHD Upper Extremity (UE) Composite Score** is calculated as the sum of the individual muscle strength average scores for the following muscle groups: gross grip, shoulder abductors, elbow flexors and elbow extensors. If a component individual muscle strength raw score is missing, the composite score will not be computed.
- **HHD Lower Extremity (LE) Composite Score** is calculated as the sum of the individual muscle strength average scores for the following muscle groups: hip flexors, hip extensors, hip abductors, hip adductors and knee flexors. Knee extensors will not be included in the calculation of the LE HHD composite score. If a component individual muscle strength raw score is missing, the composite score will not be computed.
- **HHD Total Composite Score** is calculated as the sum of the HHD UE composite score and the HHD LE composite score. If the UE or LE composite scores are missing, the HHD Total Composite Score will not be computed.
- **Predicted Normal HHD Values** will be derived for the raw right/left strength values from bilateral pinch, gross grip, shoulder abductors, elbow flexors, elbow extensors, hip flexors, hip extensors, hip abductors, hip adductors, knee flexors and knee extensors collected at Baseline using the regression equations outlined in Appendix 10.4. Predicted normal HHD scores for derived variables such as individual muscle raw score, UE/LE composite score, and total composite score will use the same computation method for raw

scores as described above but replace the observed values with the predicted normal HHD values.

- **% of Predicted Normal HHD Values** for the individual muscle groups and composite scores will be calculated as follows: (Observed Value / Predicted Normal HHD Value) \*100%. Baseline predicted normal values will be used to derive % of predicted normal values for all post-baseline study time points.

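### The female left hip-adduction slope in SAP 10.4 (0.30 per year, against 0.00 on the right) is very probably a transcription error and lowers younger women's tertiary percent-predicted hip adductor and LEC values

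*SAP*

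**What the plan says.** SAP 10.4, Hip adduction, gives predicted normal force in kgf by sex, side and age. The quoted equations below lack only their closing bracket.

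- Women aged 55 or less: left "19.1 - 0.30*(age - 55"; right "19.5 - 0.00*(age - 55".
- Women over 55: left "19.1 - 0.212*(age - 55"; the right row has the same form, with intercept 19.5 and slope 0.245.
- Men aged 49 or less: left "31.8 + 0.044*(age - 49"; right "31.6 - 0.082*(age - 49".

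Protocol 7.3.1 admits "Male or female, aged 18 – 55 years, inclusive", so no woman in the trial can use the over-55 rows.

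SAP 4.4 sets out how the predicted values are used: "The percent predicted force will be calculated for each side and the bilateral percent predicted values will be averaged for each lower extremity muscle group". Percent-predicted LEC is then the mean over five muscle groups, hip adductors being one. SAP 5.3 fixes the denominator: "Baseline predicted normal values will be used to derive % of predicted normal values for all post-baseline study time points". These outcomes are tertiary. SAP 8.8.3 limits them to summary statistics, whereas the table in SAP 10.7 lists a GEE model for them.

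**The concern.** The two female rows that matter describe two very different legs. The right-side normal does not change with age. The left-side normal falls by 0.30 kgf a year and is therefore far above the right in young women. A denominator that is too large makes percent predicted too small, and it also shrinks any change from baseline. Because the denominator is set once and reused at every visit, later data do not dilute the distortion. It applies to one sex only and grows as age falls. The outcomes concerned are the percent-predicted hip adductor value, the percent-predicted LEC, and the total percent-predicted composite in SAP 5.3 if that is reported.

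**Working it through.** The documents state no predicted value or side ratio, so there is no plan figure to reproduce. The check evaluates the printed equations.

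**1. Left against right, women.** Left = 19.1 + 0.30 × (55 − age); right = 19.5.

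| Age | Left (kgf) | Right (kgf) | Left/right − 1 |
|---|---|---|---|
| 18 | 19.1 + 11.1 = 30.2 | 19.5 | +55% |
| 30 | 19.1 + 7.5 = 26.6 | 19.5 | +36% |
| 40 | 19.1 + 4.5 = 23.6 | 19.5 | +21% |
| 50 | 19.1 + 1.5 = 20.6 | 19.5 | +6% |
| 55 | 19.1 | 19.5 | −2% |

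The sides are equal where 0.30 × (55 − age) = 0.4, which is age 53.7.

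**2. Comparison with the rest of the appendix.**

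- Men, hip adduction, ages 18 to 55: left against right runs from −11% (30.4 v 34.1 at 18) to about 0%.
- Women over 55: 18.0 v 18.3 at 60 and 15.9 v 15.8 at 70.
- Other muscle groups, women aged 18 to 55, with assumed BMI 18-35 and weight 45-90 kg: left against right (or nondominant against dominant) stays between −15% and +3%. This includes shoulder abduction, at −8% to −3%. Grip has no separate side equations.
- Women against men: at 55 the ratio is 63% on the left (19.1/30.1) and 64% on the right (19.5/30.4). At 18 the right is 57% (19.5/34.1), but the left is 99% (30.2/30.4).
- Shape: the female left side loses strength faster before 55 (0.30 a year) than after (0.212), while the right is flat before 55.
- Format: every other slope in the hip-adduction table has three decimals. Only 0.30 and 0.00 have two.

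**3. Effect on percent predicted.** The true left slope is unknown, so I take 0.00 to 0.030 as an assumed range. It gives a left normal of 19.1 to 20.2 kgf at 18, which is −2% to +4% against the right. I also assume that the right row is correct and that a woman's strength is the same fraction of normal on both sides. Then

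reported / true = ½ × (assumed left normal / printed left normal + 1).

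The fraction cancels. If all five LEC groups have the same true percent predicted, the relative effect on the mean of five is one fifth of this.

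| Age | Slope 0.00 | Slope 0.030 | Hip adductors | LEC |
|---|---|---|---|---|
| 18 | ½(19.1/30.2 + 1) = 0.816 | ½(20.21/30.2 + 1) = 0.835 | −16.5% to −18.4% | −3.3% to −3.7% |
| 30 | ½(19.1/26.6 + 1) = 0.859 | ½(19.85/26.6 + 1) = 0.873 | −12.7% to −14.1% | −2.5% to −2.8% |
| 40 | ½(19.1/23.6 + 1) = 0.905 | ½(19.55/23.6 + 1) = 0.914 | −8.6% to −9.5% | −1.7% to −1.9% |
| 50 | ½(19.1/20.6 + 1) = 0.964 | ½(19.25/20.6 + 1) = 0.967 | −3.3% to −3.6% | −0.7% |
| 55 | 1 | 1 | 0 | 0 |

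For example, a woman of 30 at a true 40% of normal throughout would be reported at about 34.4-34.9% for hip adductors and 38.9-39.0% for LEC. Forming the LEC as observed sum over predicted sum, as SAP 5.3 describes, changes little: at 18 (BMI 22, 60 kg) a true 40% becomes 38.5-38.6%, against 38.5-38.7% with the mean of five.

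Changes from baseline shrink by the same proportions, provided the change is spread evenly, relative to normal, over sides and groups.

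**The case against.** The strongest objection is that correctness depends on the normative paper cited under the table, which is not part of the documents. Implausible is not the same as wrong. The two-decimal format of 0.30 and 0.00 suggests that digits may have been lost, either when the SAP was written or when its text was read from the PDF. That stands, and it is why the point is a request to verify.

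A reader might infer that the coefficient should be 0.030. The documents do not support a particular value: slopes of 0.00, 0.003 and 0.030 all bring the sides to within about 4% of each other. Nor do they prove which row is wrong. The comparison with men points to the left row, but the right-side 0.00 shares the odd format. A reader might also set 0.30 against the male left slope of 0.044 as a sevenfold difference. That comparison fails, because the male left row rises with age.

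The consequence is limited, and this also stands. Single-side figures, such as a left-side change understated by 25% at age 30 (1 − 19.85/26.6, if the slope were 0.030), describe no reported endpoint, because the sides are averaged. No efficacy subgroup by sex or age is planned; SAP 8.9 mentions gender subgroups only for adverse events.

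**Conclusion.** The printed slope is out of line with the male rows, with the female rows after 55 and with every other left/right pair in SAP 10.4. A transcription error is very probable but not proven. Programmed as printed, it would lower percent-predicted hip adductor values by about 16-18% at age 18, 13-14% at 30 and 9-10% at 40, and percent-predicted LEC by about 3-4%, 2.5-3% and 2%. The effect is small by 50 and gone by about 54, so it does not reach all women equally.

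These sizes assume that the left slope is the wrong one, that its true value lies between 0.00 and 0.030, and that strength is the same fraction of normal on both sides and across the five groups.

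Two further inferences would go too far. The key secondary LEC is not affected: it is a sum of forces in kg and uses no reference equation, as do the primary UEC and knee extensor strength, while GNEM-FAS mobility is a functional score. And the treatment comparison is not tilted towards either arm: one formula, fixed at baseline, serves both, and randomization is stratified by gender. What suffers is the accuracy of tertiary percent-predicted results in younger women.

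**What to change.** Before programming, check both female rows for age 55 or less (slopes 0.30 and 0.00) against the normative source cited in SAP 10.4, and correct the SAP to the source values without presuming 0.030. If the source does contain 0.30 and 0.00, say so in a note under the table. Add a programming check that left and right predicted normals agree plausibly for each muscle group across ages 18 to 55.

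The cost is one look-up, at most two coefficients in an appendix and one routine check. Trial conduct, data collection and the primary and key secondary analyses do not change.

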### **Elbow flexion, elbow extension, hip flexion, hip extension, knee flexion, knee extension**

#### **Regression Equations for Strength Prediction**

Muscle Action	Equation
Right Elbow Flexion	$-(\text{age} * 0.13) + (\text{gender} * 11.24) + ((\text{weight}/\text{height}^2) * 0.07) + 22.78$
Left Elbow Flexion	$-(\text{age} * 0.11) + (\text{gender} * 10.63) + ((\text{weight}/\text{height}^2) * 0.05) + 19.66$
Right Elbow Extension	$-(\text{age} * 0.08) + (\text{gender} * 8.33) + ((\text{weight}/\text{height}^2) * 0.16) + 12.37$
Left Elbow Extension	$-(\text{age} * 0.07) + (\text{gender} * 8.18) + ((\text{weight}/\text{height}^2) * 0.17) + 11.32$
Right Hip Flexion	$-(\text{age} * 0.33) + (\text{gender} * 19.19) + ((\text{weight}/\text{height}^2) * 0.66) + 34.44$
Left Hip Flexion	$-(\text{age} * 0.29) + (\text{gender} * 18.75) + ((\text{weight}/\text{height}^2) * 0.47) + 36.05$
Right Hip Extension	$-(\text{age} * 0.21) + (\text{gender} * 15.19) + ((\text{weight}/\text{height}^2) * 0.14) + 33.52$
Left Hip Extension	$-(\text{age} * 0.23) + (\text{gender} * 15.02) + ((\text{weight}/\text{height}^2) * 0.17) + 33.88$
Right Knee Flexion	$-(\text{age} * 0.16) + (\text{gender} * 8.78) + ((\text{weight}/\text{height}^2) * 0.08) + 22.47$
Left Knee Flexion	$-(\text{age} * 0.17) + (\text{gender} * 7.67) + ((\text{weight}/\text{height}^2) * 0.14) + 21.10$
Right Knee Extension	$-(\text{age} * 0.38) + (\text{gender} * 18.44) + ((\text{weight}/\text{height}^2) * 0.62) + 34.41$
Left Knee Extension	$-(\text{age} * 0.38) + (\text{gender} * 17.68) + ((\text{weight}/\text{height}^2) * 0.62) + 33.61$

(NIMS 1996)

Strength prediction results in kilograms (kg)

Age = years; gender: male = 1, female = 0; weight = kg;; height = meters

**Note:** Age, height and weight values collected at the Baseline visit will be used for the calculation of predicted values for elbow flexion, elbow extension, hip flexion, hip extension, knee flexion and knee extension for all study time points.

## Gross Grip

### Normative grip strength values for the Jamar dynamometer for clinical use (in pounds)

Age (years)	Females (n = 355)			Males (n = 365)		
	Number of subjects	5 th %ile Jamar values (lbs)	Median Jamar values (lbs)	Number of subjects	5 th %ile Jamar values (lbs)	Median Jamar values (lbs)
20 - 29	51	50	62	50	81	100
30 - 39	50	49	64	51	80	105
40 - 49	50	48	63	50	78	107
50 - 59	51	45	61	54	73	104
60 - 69	49	40	56	58	64	95
70 - 79	50	32	46	50	51	77
≥80	54	22	34	52	34	54

(Peters et al. 2011)

**Note:** The age category that applies for a subject at the Baseline visit will be used for the calculation of predicted grip values for all study time points.

## Walking Ability

### Calculation of Predicted Six-Minute Walk Test Distance

$$6\text{MWT Distance (meters)} = 868.8 - (2.99 * \text{Age}) - (74.7 * \text{Gender})$$

Age in years. Men = 0 and Women = 1.

**Note:** The age of a subject at the Baseline visit will be used for the calculation of 6MWT predicted values for all study time points.

## Gait Speed Tests

### Mean (X) and Standard Deviation (SD) of Comfortable and Maximum Gait Speed

#### Presented by Gender and Decade of Age

COMFORTABLE GAIT SPEED (cm/sec)					MAXIMUM GAIT SPEED (cm/sec)				
	Actual		Height Normalized*		Actual		Height Normalized*		
Sex/decade	X	SD	X	SD	X	SD	X	SD	
Men									
20s	139.3	15.3	0.788	0.093	253.3	29.1	1.431	0.162	
30s	145.8	9.4	0.828	0.052	245.6	31.5	1.396	0.177	
40s	146.2	16.4	0.829	0.090	246.2	36.3	1.395	0.197	
50s	139.3	22.9	0.794	0.119	206.9	44.8	1.182	0.259	
60s	135.9	20.5	0.777	0.116	193.3	36.4	1.104	0.198	
70s	133.0	19.6	0.762	0.105	207.9	36.3	1.192	0.201	
Women									
20s	140.7	17.5	0.856	0.098	246.7	25.3	1.502	0.142	
30s	141.5	12.7	0.864	0.087	234.2	34.4	1.428	0.206	
40s	139.1	15.8	0.856	0.098	212.3	27.5	1.304	0.160	
50s	139.5	15.1	0.863	0.104	201.0	25.8	1.243	0.158	
60s	129.6	21.3	0.808	0.131	177.4	25.4	1.107	0.157	
70s	127.2	21.1	0.807	0.131	174.9	28.1	1.110	0.176	

(Bohannon 1997a)

\* actual speed (cm/s)/height (cm).

**Note:** Height normalized values will be used for the calculation of predicted comfortable and maximum gait speeds. The age category (in decades) of a subject at the Baseline visit will be used for the calculation of comfortable and maximum gait speed predicted values for all study time points.

## 10.5 Patient-reported Outcomes

### Individual Neuromuscular Quality of Life Questionnaire (INQoL)

Dimensions	Subscales	Number of Items	Cluster of Items	Item Reversion	Direction of Dimensions
Symptoms	Weakness	3	1 a, b, c	No	
	Locking	3	2 a, b, c		
	Pain	3	3 a, b, c		
	Fatigue	3	4 a, b, c		
Life domains	Activities	5	5 AI, II, III 5 BI, II	No	Higher scores = higher impact
	Independence	3	6A, 6BI, 6BII		
	Social relationships	10	7AI, II, III, IV 7 BI, II, III, IV, V, VI		
	Emotions	6	8AI, II, III, IV, BI, II		
	Body image	3	9A, 9BI, II		
Treatment effects (not included in this study)	Perceived treatment effects	3	10AI, III 10BI, III	No	
	Expected treatment effects	3	10AII, AIII, 10BII, III		
Quality of life	NA	14	Items from section B for questions 5 to 9	No	

## SCORING OF DIMENSIONS:

Item Scaling	7-point Likert scale from 1 to 7 for items 1a, 2a, 3a, 4a 7-point Likert scales from 0 to 6 : for all other items
Weighting of items	Yes. Please see the scoring procedure below
Extension of the scoring scale	0-100
Scoring Procedure	
 
1. Weakness score = <math>(a+b+c) / 19 \times 100</math>
 
2. Muscle 'locking' score = <math>(a+b+c) / 19 \times 100</math>
 
3. Pain score = <math>(a+b+c) / 19 \times 100</math>
 
4. Fatigue score = <math>(a+b+c) / 19 \times 100</math>
 
5. Activities score = <math>[4 \times (AI+AII+AIII)] + [3 \times (BI+BII)] / 108 \times 100</math> 
If not working due to condition item → AIII=6
 
If retired/unemployed/work in home (not as a result of condition)
 
→ <math>[6 \times (AI+AII)] + [3 \times (BI+BII)] / 108 \times 100</math>
 
 
6. Independence score = <math>[12 \times A] + [3 \times (BI+BII)] / 108 \times 100</math>
 
7. Social relationships = <math>[3 \times (AI+AII+AIII+AIV)] + [BI+II+III+IV+V+VI] / 108 \times 100</math> 
If partner/spouse item (AI) not applicable:
 
→ <math>[4 \times (AII+AIII+AIV)] + [BI+II+III+IV+V+VI] / 108 \times 100</math>
 
 
8. Emotions score = <math>[3 \times (AI+AII+AIII+AIV)] + [3 \times (BI+BII)] / 108 \times 100</math>
 
9. Body Image score = <math>[12 \times (A)] + [3 \times (BI+BII)] / 108 \times 100</math>
 
10. Qol score: Add scores of items in section B for questions 5-9 (with correction i.e. 3X (BI + B2) for Quns 5,6,8&9 and BI+II+III+IV+V+VI for Qun 7), divide total score by 180 and multiply by 100 (to achieve percentage score)
 

Interpretation and Analysis of missing data	
Quns 1-4
 
1A-4A If missing and rest of symptom qun missing (i.e. part B) → score zero
 
1B-4B a. If missing, score “1”
 
    b. If missing, impute previous value (part a)
 
    c. If missing, score “0”
 
Qun 5
 
5 A. If an item missing, sum completed items, and multiply by 6 if two items completed and 12 if only one item has been completed (to get score out of 72)
 
(N.B. “Work activities” item: if not working due to condition score “6” and count as a completed item).
 
EXAMPLE: If “Leisure activities” is missing, add values of “Daily activities” & “Work Activities”. Multiply this by 6.
 
    BI. If missing, impute average of completed “activities” items (from 5A)
 
    BII. If missing, score as “0”
 
Qun 6
 
6 A. if missing, score as “0”
 
    BI. If missing, impute value from 6A
 
    BII. If missing, score as “0”
 
Qun 7
 
7 A. If item missing, sum the completed items and multiply by 4 if three completed items, 6 if two completed items & 12 if one completed item
 
    BI. If missing, impute average of 7a items
 
        i) Relationship with spouse/partner &
 
        ii) Relationship with other family members
 
    BII. If missing, score as “0”
 
    BIII. If missing, impute value from “Friends” (7AII) item
 
    BIV. If missing, score as “0”
 
    BV. If missing, impute value from “Other people” (7AIV) item
 
    BVI. If missing, score as “0”

---	--

	
Qun 8
 
8 A. If item missing, sum the completed items and multiply by 4 if three completed items, 6 if two completed items and 12 if one completed item
 
BI. If missing, impute average of items completed in 8A
 
BII. If missing, score as “0”
 
Qun 9
 
A. If missing, score as “0”
 
BI. If missing, impute value from 9a
 
BII. If missing, score as “0”
 
Qun 10 (not included in this study)
 
10A I. If missing, score as “0”
 
II. If missing, score as “0”
 
III. If missing, score as “0”
 
10B I. If missing, score as “0”
 
II. If missing, score as “0”
 
III. If missing, score as “0”

--	--

(Vincent et al. 2007).

**Note:** Question #10 dealing with treatment effects was not administered or scored as part of this study due to the double-blind study design.

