#### 5.4 Patient Reported Outcomes

- **GNEM Functional Activities Scale (GNEM-FAS) Total Score** will be calculated as the sum of the Total Scores range from 0 to 100 with higher scores representing greater independence with functional activities. Subscale scores will be calculated for the Mobility, Upper Extremity and Self-Care domains. Mobility subscale scores range from 0 to 40 with higher scores representing greater mobility. Upper Extremity subscale scores range from 0 to 32 with higher scores representing more skilled, independent use of the arms during functional activity performance. Self-Care subscale scores range from 0 to 28 with higher scores representing greater independence with functional care activities.
- **Individual Neuromuscular Quality of Life Scale (INQoL) Subscale and QoL:** The individual domain scores will be calculated using the scoring algorithms outlined in Appendix 10.5 Derived Variables.
- **Number of doses administered** will be calculated for each subject by summing the number of doses administered over all visits.
- **Prior medications** include all medications taken by the subject from 30 days prior to the signing of the informed consent until the first dose of study medication is administered.
- **Concomitant medications** include all medications that are taken after the first dose of study medication is administered.

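### The INQoL life-domain formulas in SAP Appendix 10.5 lack an outer bracket; coded as printed they reach 105.3 on a 0-100 scale, with little effect on the tests

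*SAP*

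**What the plan says.** SAP Section 5.4 delegates INQoL scoring to the appendix: "The individual domain scores will be calculated using the scoring algorithms outlined in Appendix 10.5 Derived Variables". Within Appendix 10.5, the scoring-of-dimensions box fixes the range: "Extension of the scoring scale 0-100". It scores every item outside the first item of each symptom question on "7-point Likert scales from 0 to 6".

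The box then prints seven expressions for the five life domains. The quotes below start just after each opening square bracket.

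- Activities: "4 \times (AI+AII+AIII)] + [3 \times (BI+BII)] / 108 \times 100"
- Activities, for subjects not working for reasons other than the condition: "6 \times (AI+AII)] + [3 \times (BI+BII)] / 108 \times 100"
- Independence: "12 \times A] + [3 \times (BI+BII)] / 108 \times 100"
- Social relationships: "3 \times (AI+AII+AIII+AIV)] + [BI+II+III+IV+V+VI] / 108 \times 100"
- The alternative Social relationships line (partner item not applicable), Emotions and Body image follow the same pattern.

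In the same box, the four symptom lines put their numerator in parentheses before dividing by 19. The QoL line says in words that the total is divided by 180. Protocol Section 7.5.2.7 describes the questionnaire but gives no scoring formula, and neither document prints the life-domain lines in another form.

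**The concern.** Each life-domain line has the form [A part] + [B part] / 108 × 100. Under ordinary operator precedence the division and the multiplication act on the B part alone, and the A part is added unscaled. The result contradicts the 0-100 range in the same box.

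This needs no missing item, so it is separate from the missing-item rules later in the appendix. At stake are the reported levels and mean differences for five subscales of a tertiary endpoint (SAP Sections 4.4 and 8.8.3). A literal transcription would run without error, and a range check on the data would seldom expose it.

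**Working it through.** **Inputs (SAP Appendix 10.5).** Life-domain items run from 0 to 6. The weights are those printed. The stated range is 0-100.

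**Step 1: maximum of each part.**

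| Line | A part | B part |
|---|---|---|
| Activities | 4 × 18 = 72 | 3 × 12 = 36 |
| Activities, alternative | 6 × 12 = 72 | 3 × 12 = 36 |
| Independence | 12 × 6 = 72 | 3 × 12 = 36 |
| Social relationships | 3 × 24 = 72 | 36 |
| Social relationships, alternative | 4 × 18 = 72 | 36 |
| Emotions | 3 × 24 = 72 | 3 × 12 = 36 |
| Body image | 12 × 6 = 72 | 3 × 12 = 36 |

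**Step 2: can the stated range be reproduced?**

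- As printed: 72 + (36 / 108) × 100 = 72 + 33.33 = 105.33. It cannot.
- With an outer bracket: (72 + 36) / 108 × 100 = 100. It can, for all seven lines.
- For comparison, a symptom line gives (7 + 6 + 6) / 19 × 100 = 100, and the QoL line gives (4 × 36 + 36) / 180 × 100 = 100. Both are right as written.

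The intended grouping is clear. 108 equals 72 + 36, and the missing-item rule for question 5 rescales its A part to a score out of 72.

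**Step 3: size of the error.** Let a and b be the A and B parts as fractions of their maxima.

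- Printed = 72a + 33.33b
- Intended = (72a + 36b) / 108 × 100 = 66.67a + 33.33b
- Printed minus intended = 5.33a, that is 5.33 × (A part / 72)

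With every item at 3 (a = b = 0.5), the printed line gives 36 + 16.67 = 52.67 and the intended one 50.0. With all A items at 0 there is no error.

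A-item coefficients are 72 / 66.67 = 1.08 times the intended ones (for Activities, 4 instead of 4 / 1.08 = 3.70). B-item coefficients are unchanged. The A share of the maximum is 72 / 105.33 = 68.4% instead of 66.7%, so this is not a pure change of unit.

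**Step 4: mean differences.** Suppose the arms differ by 0.5 point per item on Activities.

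- All five items: printed 4 × 1.5 + 3 × 1 / 108 × 100 = 6.00 + 2.78 = 8.78; intended (6 + 3) / 108 × 100 = 8.33. The ratio is 1.053.
- A items only: printed 6.00; intended 6 / 108 × 100 = 5.56. The ratio is 1.08.

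**Step 5: effect on the tests.** Changes from baseline are the same linear combinations, in both arms. Assume the changes in a and b have equal variance and correlation r, neither of which the documents give. In units of that variance:

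- r = 0: variances 72² + 33.33² = 6295 (printed) and 66.67² + 33.33² = 5556 (intended); covariance 72 × 66.67 + 33.33² = 5911. The correlation of the two scores is 5911 / √(6295 × 5556) = 0.9995. The SD ratio is √(6295 / 5556) = 1.064.
- r = 0.5: variances 8695 and 7778, covariance 8222, correlation 0.9998, SD ratio 1.057.
- r = -0.5: variances 3895 and 3333, covariance 3600, correlation 0.999.

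At r = 0 to 0.5, the difference divided by its SD changes by a factor of 1.053 / 1.064 = 0.99 to 1.053 / 1.057 = 1.00 if all items move. If only A items move, the factor is 1.08 / 1.064 = 1.01 to 1.08 / 1.057 = 1.02.

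**Step 6: would a range check find it?** An Activities pattern exceeds 100 as printed only when it falls short of 105.33 by less than 5.33 points. That allows all items at maximum (1 pattern), one A item one step lower (3 patterns, -4) or one B item one step lower (2 patterns, -2.78). This makes 6 of 7⁵ = 16,807 complete patterns.

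**The case against.** The strongest reply is that nobody would code it this way. The stated range, the 72 in the question 5 rule and 72 + 36 = 108 identify the intent, and the box is shorthand rather than program code. This stands as to consequence: the error bites only if the line is coded literally. It does not make the text right, because Section 5.4 names this appendix as the algorithm and no correct version appears elsewhere.

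A second reply is that a stacked fraction may have been flattened when the PDF was read. That cannot be excluded. It is less likely given that the symptom lines keep parentheses around their numerator, which inline typesetting needs and a stacked fraction does not.

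A reader might go further and infer that the scores would be wrong for every completed questionnaire, that treatment effects would be spuriously favourable, or that the subscales could no longer be compared with each other. The documents do not support this:

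- The error is zero when all A items are 0.
- The same formula applies to both arms, so it creates no effect where none exists, and the standard error grows with the difference.
- No comparison between subscales is planned. SAP Section 8.8.3 tests each tertiary endpoint separately at a nominal level.
- How many INQoL scores will be analysed is not settled. SAP Section 4.4 speaks of four domains and Section 10.7 of a total score. The count of nine administered subscales, of which these are five, comes from Protocol Section 7.5.2.7 and the dimension table in Appendix 10.5.

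**Conclusion.** The seven life-domain lines are wrong as written, and the severity is low. Followed literally, they put five tertiary subscales off their stated scale: by up to 5.33 points in level, and by 5.3% to 8% in mean differences when all items or only A items move. These percentages assume that A and B items do not move in opposite directions. P-values would hardly change: the printed and intended scores correlate at about 0.999 or higher under the assumptions in the working. The symptom scores, the QoL score (which uses B items only) and the primary and key secondary endpoints are untouched. The size of the error rests on arithmetic alone; whether it occurs depends on how the line is programmed.

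**What to change.** In SAP Appendix 10.5, write each of the seven lines as ([A part] + [B part]) / 108 × 100, including the alternative Activities and Social relationships lines. Add a programming check, on every branch of the life domains, that all items at maximum return exactly 100 and all items at zero return 0. The all-maximum case is the one that detects this error, since the printed form also returns 0 at zero. Do not apply the zero check to the symptom lines: their first item starts at 1, so their lowest complete score is 1 / 19 × 100 = 5.26. The cost is SAP wording and a short test, with no new data and no change to any other endpoint.
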